## Questionnaires for individual characteristics

Several validated questionnaires that have previously been related to expectancy learning mechanisms will be completed by the participants to assess the role of individual characteristics on expectancy effects on itch [3,14,24].

## Genotype

DNA will be isolated from the saliva samples collected in Oragene tubes and 5-HTTLPR (variable number tandem repeat (VNTR)) genotyping will be conducted by PCR and subsequent analysis of product lengths, as we performed previously (CMO registration number 2010/ 450). Additional genotypes will be tested on the longer term, by either classical genotyping or next generation sequencing techniques.

## **Debriefing**

Participants will be debriefed after completion of the experiment and informed about the purpose of the study. Participants will be given the opportunity to ask questions they have regarding the experiment and their participation in it.

## 8.4 Withdrawal of individual subjects

Subjects can leave the study at any time for any reason if they wish to do so without any consequences. The investigator can decide to withdraw a subject from the study for urgent medical reasons.

## 8.4.1 Specific criteria for withdrawal (if applicable)

Not applicable.

### 8.5 Replacement of individual subjects after withdrawal

As in our previous studies, in which withdrawal of subjects was highly uncommon [e.g., 3, 25], also in the present study low withdrawal is expected (e.g., due to apparatus not functioning properly). Participants who have withdrawn from the study or for which data loss will occur, will be replaced by randomly selected additional participants with a maximum 10%.

#### 8.6 Follow-up of subjects withdrawn from treatment

Not applicable.

## 8.7 Premature termination of the study

Not applicable.

#### 9. SAFETY REPORTING

#### 9.1 Section 10 WMO event

In accordance to section 10, subsection 1, of the WMO, the investigator will inform the subjects and the reviewing accredited METC if anything occurs, on the basis of which it appears that the disadvantages of participation may be significantly greater than was foreseen in the research proposal. The study will be suspended pending further review by the accredited METC, except insofar as suspension would jeopardise the subjects' health. The investigator will take care that all subjects are kept informed.

#### 9.2 AEs, SAEs and SUSARs

#### 9.2.1 Adverse events (AEs)

Adverse events are defined as any undesirable experience occurring to a subject during the study, whether or not considered related to [the investigational product / the experimental interventiont]. All adverse events reported spontaneously by the subject or observed by the investigator or his staff will be recorded.

## 9.2.2 Serious adverse events (SAEs)

A serious adverse event is any untoward medical occurrence or effect that at any dose:

- results in death;
- is life threatening (at the time of the event);
- requires hospitalisation or prolongation of existing inpatients' hospitalisation;
- results in persistent or significant disability or incapacity;
- is a congenital anomaly or birth defect;
- Any other important medical event that may not result in death, be life threatening, or require hospitalization, may be considered a serious adverse experience when, based upon appropriate medical judgement, the event may jeopardize the subject or may require an intervention to prevent one of the outcomes listed above.

The sponsor will report the SAEs through the web portal *ToetsingOnline* to the accredited METC that approved the protocol, within 15 days after the sponsor has first knowledge of the serious adverse reactions.

SAEs that result in death or are life threatening should be reported expedited. The expedited reporting will occur not later than 7 days after the responsible investigator has first knowledge of the adverse reaction. This is for a preliminary report with another 8 days for completion of the report.

## 9.2.3 Suspected unexpected serious adverse reactions (SUSARs)

Not applicable.

## 9.3 Annual safety report

Not applicable.

### 9.4 Follow-up of adverse events

All AEs will be followed until they have abated, or until a stable situation has been reached. Depending on the event, follow up may require additional tests or medical procedures as indicated, and/or referral to the general physician or a medical specialist.

SAEs need to be reported till end of study within the Netherlands, as defined in the protocol

## 9.5 [Data Safety Monitoring Board (DSMB) / Safety Committee]

Not applicable.

#### 10. STATISTICAL ANALYSIS

### 10.1 Primary study parameter(s)

All variables are continuous. Descriptive statistics (means, standard deviations, etc.) will be calculated of all relevant variables. Variables will be checked for outliers and skewness as these can severely limit the usefulness of the mean as measure for location.

In consultation with the statistician associated with the study ([name]), our main hypothesis, that the induced levels of itch (VAS) will be lower after a positive expectation induction (low-itch expectation induction) (group 1), in comparison to a negative expectation induction (high-itch expectation induction) (group 2), or neutral expectation induction (group 3), will be tested in an ANOVA using Dunnett contrasts for comparing the expectancy effect on itch in group 1 with the effect in group 2 and group 3.

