### 4.4 Sample size calculation

The required sample size was calculated, in agreement with a statistician ([name], Radboudumc), based on our previous study with a comparable design [25]. Such as in the present study, in our previous study a comparison was made between a positive expectation induction by conditioning and verbal suggestion and a control group. In this study an average placebo effect of 0.86 (SD = 0.59) and 0.32 (SD = 0.79) was found in the *conditioning with verbal suggestion group* and the *control group*, respectively (effect size of d = 0.78). Based on these means and standard deviations, sample size calculations were done using G\*power 3.1. We simplified the analyses of the main hypotheses, Univariate analyses of variance (ANOVA's) with Dunnett contrasts, into two two-tailed independent samples t-tests (i.e., comparing the positive expectation induction group with the negative expectation induction group and the neutral expectation induction group separately) using a Bonferroni correction. For these t-tests, the means and standard deviations of the most conservative comparison in the present study were used, i.e., of the positive expectation induction with the neutral expectation induction. With an effect size of d = 0.78, an alpha of 0.025 and a desired power of 0.80, this resulted in an estimated total sample size of 33 participants per group.

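### A step-down form of the Dunnett test in section 10.1 would add about 4 to 6 points of power for the group 1 versus group 3 contrast at the same 5% familywise error and 33 per group (an efficiency gain, not an error)

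*Protocol*

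**What the plan says.** Section 10.1 fixes the primary test. The hypothesis of lower itch after the low-itch induction "will be tested in an ANOVA using Dunnett contrasts for comparing the expectancy effect on itch in group 1" with groups 2 and 3. No step-down, Holm, closed or ordered procedure is named.

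Section 4.4 simplifies this, for sizing, "into two two-tailed independent samples t-tests" (group 1 against each control group separately), "using a Bonferroni correction". It takes group 1 versus group 3 as the reference case: "the means and standard deviations of the most conservative comparison in the present study were used". The inputs are a mean effect of 0.86 (SD 0.59) against 0.32 (SD 0.79). "With an effect size of d = 0.78, an alpha of 0.025 and a desired power of 0.80", it arrives at 33 per group. The total of 99 (3 × 33) and the familywise 5% (2 × 0.025) follow from these figures but are not printed.

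**The concern.** A single-step rule holds each contrast to the full two-comparison critical value, whatever the other contrast shows. Once one of two hypotheses has been rejected, only one remains that could be falsely rejected, and it can be tested at two-sided 5% without raising the familywise error. Single-step Dunnett never uses this.

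The plan's own premise is the situation in which this matters. If group 1 versus group 3 is the most conservative comparison, group 1 versus group 2 is expected to show at least as large a difference. It will then usually be rejected, which frees the full 5% for group 1 versus group 3. At stake are a few points of power on the contrast used for sizing, available without extra participants.

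**Working it through.** **Inputs.** Means 0.86 and 0.32, SDs 0.59 and 0.79, 33 per group, two-sided, 0.025 per contrast (all section 4.4). Not in the protocol and therefore assumed: the group 2 mean effect (0.60, 0.32, and 0 or below, on the section 4.4 scale, where a positive value favours less itch) and the group 2 SD.

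**Reproducing the plan's figure.** Common SD = √((0.59² + 0.79²)/2) = 0.697, so d = 0.54/0.697 = 0.7745; the plan prints 0.78. For a two-sided two-sample t-test at 0.025 with d = 0.78, noncentral-t power is 0.792 at 32 per group and 0.806 at 33. The stated 33 reproduces. At d = 0.7745 the power at 33 is 0.800.

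**Critical values with the ANOVA error term (df = 99 − 3 = 96).**
- Dunnett, two contrasts, correlation 0.5, two-sided 5%: about 2.245, which is 0.0271 per contrast.
- Bonferroni 0.025: 2.277.
- Unadjusted two-sided 0.05: 1.985.

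**Single-step power, group 1 versus group 3.** Noncentrality = 0.7745 × √(33/2) = 3.146. Against 2.245 the power is 0.815. Against 1.985, the most a step-down rule could reach, it is 0.876.

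**Step-down rule.** Test the larger |t| against 2.245; if it is rejected, test the other against 1.985. Power for group 1 versus group 3 at 33 per group (simulation, at least 1,000,000 trials per scenario; group 2 SD taken as the common SD or as 0.79):

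| Group 2 mean effect (assumed) | Common SD 0.697: single-step → step-down | SDs 0.59/0.79/0.79: single-step → step-down |
|---|---|---|
| 0.60 (contrary to the plan's expectation) | 0.815 → 0.819 | 0.786 → 0.793 |
| 0.32 (equal to group 3) | 0.815 → 0.856 | 0.786 → 0.833 |
| 0 or below | 0.815 → 0.876 | 0.786 → 0.856 |

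Holm (0.025, then 0.05) gives 0.852 and 0.876 in the second and third rows with a common SD.

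**Type II error, common SD.** 18.5% single-step against 14.4% step-down (18.5/14.4 = 1.28) or 12.4% (18.5/12.4 = 1.49). The single-step rule's type II error is thus about 28% to 50% higher.

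**Familywise error of the step-down rule, common SD.** 5.0% when both nulls are true, and 5.0% when group 1 versus group 2 is a large true difference and group 1 versus group 3 is null.

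**What does not change.** The first step is the single-step test, so the probability of at least one rejection is identical: 0.921 under both rules with group 2 at 0.32.

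**If both contrasts must be significant (group 2 at 0.32).** Single-step gives about 0.71, step-down 0.791, and each contrast at an unadjusted 0.05 gives 0.797.

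**Equivalent sample size, at d = 0.78.** Step-down power is 0.861 (group 1 versus group 2 effect also 0.78) to 0.881 (that effect 1.5). Single-step Dunnett needs 37 to 39 per group to match, that is (37 − 33) × 3 = 12 to (39 − 33) × 3 = 18 more participants.

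**The case against.** The strongest reply is that nothing here is wrong. Dunnett is the standard method for comparing one group with two others, it controls the familywise error, it was chosen with the study statistician, and the plan reaches its 80% target. This stands, and the point is an optional improvement. It also stands that the protocol does not print the word single-step. That is the ordinary reading of Dunnett contrasts, supported by the Bonferroni sizing, but an analysis plan not at hand could specify a stepwise form.

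Single-step Dunnett also has a merit: its simultaneous confidence intervals always agree with its tests. Under step-down, a |t| for group 1 versus group 3 between 1.985 and 2.245 can be declared significant while the single-step interval still covers zero. Section 10.1 plans no such intervals, so the loss is small but real.

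Four stronger readings might be inferred, and the documents do not support them:
- That the trial becomes more likely to succeed under any definition of success. Sections 8.1.1 and 10.1 join the two comparisons with the word or. If either contrast suffices, step-down changes nothing; if both are needed, no adjustment is required at all.
- That group 1 versus group 3 carries the answer. Sections 2, 8.1.1 and 10.1 give the two comparisons equal standing; section 4.4 singles this one out for sizing only.
- That the sample could be cut to 27 per group. Power there is about 0.77 with group 2 at 0.32, and also about 0.77 with unequal SDs and group 2 at 0.
- That type II error is always inflated by half. This is the favourable case; at the bound that section 4.4 supports, it is about 28%.

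**Conclusion.** The point holds as a cheap efficiency improvement. For a separate claim on group 1 versus group 3, the step-down form adds about 4 points of power if group 2's effect equals group 3's (0.815 to 0.856) and about 6 points if it is at or below 0 (0.815 to 0.876). With SDs of 0.59/0.79/0.79 the rise is from 0.786 to between 0.833 and 0.856.

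This rests on the plan's means, 33 analysed per group, and an assumed group 2 effect no better than group 3's, which is what section 4.4 implies by calling group 1 versus group 3 the most conservative comparison. If group 2's effect were near 0.60, the gain would be under 1 point. It is never negative. The existing plan remains valid and meets its power target on its own sizing assumptions.

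**What to change.** In section 10.1, specify step-down Dunnett: compare the larger of the two |t| values with the two-comparison Dunnett critical value (about 2.24 at 96 df) and, if it is rejected, test the other contrast at two-sided 0.05. Holm (0.025, then 0.05) is a simpler alternative with nearly the same power. If the intended claim requires both contrasts, say so and test each at two-sided 0.05 instead.

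In section 4.4, keep 33 per group. Add that power for group 1 versus group 3 under the step-down rule is about 0.86 to 0.88 with a common SD (0.83 to 0.86 with SDs 0.59/0.79/0.79), given a group 2 effect no better than group 3's.

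The cost is one sentence in each section, with no extra participants and no change of procedure. If single-step simultaneous intervals are reported, note that they may not always match the step-down decision.

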Study design: In healthy subjects, expectations with regard to electrically evoked itch will be induced by a conditioning with verbal suggestion procedure, in correspondence to a previous experiment conducted by the research group (25). For every stimulus, participants are asked to report the level of itch on a Visual Analogue Scale (VAS), and the scratching behavior of the participants will be recorded during the experiment. In part I, in all participants high-itch expectations will be induced (nocebo induction). More specifically, in the learning phase, short-lasting itch stimuli of medium and high intensity are repeatedly associated with certain colored cues displayed on a computer screen (e.g., two colored cues of which one cue is associated with itch stimuli of medium intensity (neutral cue), and the other with itch stimuli of high intensity (conditioned cue)). In line with the conditioning procedure, verbal suggestions for high itch will be given regarding itch stimuli associated with the conditioned cue. Subsequently, in the testing phase, expectancy effects for itch with regard to the colored cues will be tested by applying both the conditioned and neutral cues with itch stimuli of medium intensity. In part II, participants will be randomly assigned to one of three groups: the experimental group, in which lowitch expectations will be induced (group 1) (similar to the procedure described above with the exception that the conditioned cues are now associated with low itch intensity stimuli), a control group in which once more high-itch expectations will be induced similar to part I (group 2), or a control group with a neutral itch induction procedure (neutral expectation induction) (group 3). In part III, generalization of the induced expectancy effects will be tested with respect to another itch stimulus, i.e., histamine iontophoresis.

Study population: Healthy human volunteers, aged between 18 - 35 years old.

Intervention (if applicable): Not applicable.

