Main study parameters/endpoints: The main study endpoint is the difference in the levels of itch (VAS scores) evoked by the electrical stimuli associated with the conditioned cues versus the neutral cues in the testing phase of part II of the experiment. It is investigated whether nocebo effects (negative expectation effects) can be modified by a positive expectation induction by conditioning and verbal suggestion (low-itch expectation induction) (group 1), resulting in lower itch VAS scores than a repeated negative expectation induction (high-itch expectation induction) (group 2), or a neutral procedure (neutral expectation induction) (group 3).

Nature and extent of the burden and risks associated with participation, benefit and group relatedness: Participants will complete a series of validated questionnaires at home to assess relevant individual characteristics, for approximately half an hour. Participants will then visit the department of Health-, Medical & Neuropsychology at the Leiden University once for approximately 5,5 hours. Sensations of itch will be induced using frequently applied, validated stimuli of short duration which are not burdensome (e.g., [1-4], 25). DNA is collected by asking participants to spit in a special tube. No risks are involved with participation in this study, only an investment of time.

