#### 2. OBJECTIVES

## **Primary objective:**

The primary objective of the study is to determine whether induced negative expectation effects for itch can be modified. It is hypothesized that levels of itch (VAS) will be reduced after a low-itch expectation induction, in comparison to the control procedures in which high-itch expectations or neutral expectations will be induced.

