### 8.2 Randomisation, blinding and treatment allocation

After part I, in which all participants are exposed to the same procedure, in part II participants will be randomly allocated to one of three experimental groups (see section 3. Study design and Fig 1.). We will use a single blind design: Since the instructions given to the subjects differ in accordance with the group the subjects are allocated to, only subjects will be blinded for the randomization to different groups. No indications for breaking the randomization code are indicated.

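### The primary ANOVA in section 10.1 has no covariate, although the Part I effect is a pre-randomisation baseline of the primary endpoint; this may cost precision but does not cause bias

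*Protocol*

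**What the plan says.** **Endpoint.** The Protocol Summary defines the main endpoint as the "difference in the levels of itch (VAS scores) evoked by the electrical stimuli associated with the conditioned cues versus the neutral cues", taken in the testing phase of Part II. Section 8.1.1 agrees.

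**Primary model.** Section 10.1 specifies an "ANOVA using Dunnett contrasts for comparing the expectancy effect on itch in group 1 with the effect in group 2 and group 3". It names no covariate, change score or repeated-measures term. Section 4.4 sizes the trial on the matching two-sample t-tests: "With an effect size of d = 0.78, an alpha of 0.025 and a desired power of 0.80", giving 33 per group.

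**What Part I yields.** Everyone receives the high-itch induction. In the testing phase that follows, "expectancy effects for itch with regard to the colored cues will be tested by applying both the conditioned and neutral cues" at medium stimulus intensity (Summary, study design). Section 8.3 has itch rated from 0 to 10 after each stimulus. For group 1, Part II is described as "similar to the procedure described above with the exception that the conditioned cues are now associated with low itch intensity stimuli", and section 3 keeps the same coloured cue as the conditioned one.

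**Timing.** Section 8.2: "After part I, in which all participants are exposed to the same procedure, in part II participants will be randomly allocated" to the three groups.

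**Aim.** Section 2 sets out to "determine whether induced negative expectation effects for itch can be modified", and frames the hypothesis as a comparison of group 1 with the two control procedures.

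**The concern.** The Part I testing-phase difference uses the same scale, cues and stimulus level as the primary endpoint. It is recorded in every participant and precedes allocation, so it cannot be affected by group. A covariate of that kind can normally be used at almost no cost.

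Section 1 itself expects expectancy effects to vary with personality and genotype. Such stable traits would act in both parts, so some Part I-Part II correlation is plausible. If it exists, the unadjusted ANOVA leaves that predictable variation in the error term. The trial is planned at barely 80% power per contrast, so the confidence intervals and power of the two primary contrasts are at stake.

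**Working it through.** **Inputs.** Section 4.4 gives means 0.86 and 0.32, SDs 0.59 and 0.79, d = 0.78, two-sided alpha 0.025 per comparison and 33 per group. The within-group correlation r between the Part I and Part II differences is not given, so it is an assumption and is varied.

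**Step 1: reproduce the plan's figure.** Pooled SD = √((0.59² + 0.79²)/2) = 0.697, so d = 0.54/0.697 = 0.774, against 0.78 stated. The noncentrality is d√(n/2) = 0.78 × √16.5 = 3.17. A two-sample t-test with 64 df then has power 0.806 at 33 per group and 0.792 at 32. The stated 33 is correct, also with d = 0.774 (power 0.800).

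**Step 2: the planned three-group model.** With the error variance pooled over 99 participants (96 df), per-contrast power is 0.812.

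**Step 3: add the Part I difference with a common slope.** The residual variance is multiplied by (1 − r²), so the effective d is 0.78/√(1 − r²), with 95 df.

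| Assumed r | Effective d | SE factor √(1 − r²) | Power |
|---|---|---|---|
| 0 | 0.780 | 1.000 | 0.812 |
| 0.2 | 0.796 | 0.980 | 0.829 |
| 0.3 | 0.818 | 0.954 | 0.850 |
| 0.4 | 0.851 | 0.917 | 0.879 |
| 0.5 | 0.901 | 0.866 | 0.914 |
| 0.6 | 0.975 | 0.800 | 0.952 |

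At r = 0 the lost degree of freedom moves power from 0.8120 to 0.8119. At r = 0.5 the gain is worth 1/(1 − 0.25) = 1.33 times the sample. With the Dunnett critical value (about 2.24) instead of the Bonferroni one, the pattern is the same: 0.82 unadjusted, 0.86 at r = 0.3 and 0.92 at r = 0.5.

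**Step 4: unequal slopes.** Take unit variance in both parts and assumed slopes for groups 1, 2 and 3. A common-slope model fits roughly the average slope.
- Slopes −0.5, 0.5, 0: the average is 0, so nothing is adjusted.
- Slopes −0.3, 0.5, 0.3: the average is b = 0.167. The residual variance in a group with slope β is 1 − 2bβ + b², which is 1.128 in group 1 and 0.928 in group 3. Their sum is 2.056, against 2 unadjusted.

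Simulation of the group 1 versus 3 contrast agrees: power was about 0.80 and 0.81 respectively, so there is no gain. A mean-centred covariate with a group interaction gave about 0.86 and 0.85.

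**Step 5: a raw change score (Part II minus Part I).** With equal SDs its variance is 2(1 − r) times the original, which is below 1 only if r exceeds 0.5. On the t-test basis of Step 1, power is 0.65 at r = 0.3, 0.81 at r = 0.5 and 0.96 at r = 0.7.

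**The case against.** **The plan contains no error of validity.** This stands. Allocation is random and follows Part I, so the Part II contrasts are unbiased, and sections 4.4 and 10.1 agree with each other.

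**The gain rests on an unknown r and on equal slopes.** This also stands. At r = 0.2 the gain is under 2 points of power. Equal slopes are doubtful by design: group 1 reverses the training on the same cue, group 2 repeats it and group 3 has none. Strong learners might respond strongly in whichever direction they are trained. The slopes in Step 4 are as much an assumption as r is.

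**Covariates can be left to a SAP.** This stands only in part. A SAP may exist, but section 10.1 already names the model, and a covariate added later would depart from it.

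**Stronger readings that the documents do not support.**
- A reader might infer that the unadjusted ANOVA fails to answer whether a nocebo effect is modified. Section 2 poses that question between groups, and all groups share the same Part I induction. The randomised Part II contrast therefore already estimates it. The ANCOVA aims at the same mean difference with, at best, a smaller standard error.
- A reader might infer that chance imbalance in Part I invalidates the contrasts, or that adjustment removes it entirely. The ANOVA standard error already allows for chance imbalance, and adjustment removes only the linearly predictable share of variance, r² (9% at r = 0.3).
- A reader might want cue colour added to the primary model. Section 8.3 counterbalances it, and no figure in the documents supports requiring it.

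**Conclusion.** The point holds as a matter of efficiency. Section 10.1 leaves out a pre-randomisation baseline of its own primary endpoint that is already collected on everyone. The planned test is valid, its sample size is right, and the question answered would not change.

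Under a common slope the benefit is roughly 2 points of power at r = 0.2, 4 at r = 0.3 and 10 at r = 0.5, starting from 0.81. It is essentially nil at r = 0, and may be nil at any overall correlation if slopes differ in sign between groups. These figures rest on the protocol's d = 0.78, 33 complete participants per group, and an r that the documents do not supply. The change is worth making because its expected cost is negligible, not because a particular gain has been shown.

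**What to change.** Amend section 10.1 before any outcome data are examined:

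1. Make the primary analysis an ANCOVA of the Part II testing-phase difference (conditioned minus neutral VAS) on group, with the mean-centred Part I testing-phase difference as covariate.
2. Keep the Dunnett contrasts of group 1 with group 2 and with group 3, and keep 33 per group.
3. Prespecify a model with a group-by-Part I interaction, with the contrasts evaluated at the overall Part I mean, to cover unequal slopes. State in advance whether it is the primary form or a supporting analysis. If it is primary, specify a standard error that allows for unequal residual variances and for the Part I mean being estimated.
4. Report the unadjusted ANOVA as a sensitivity analysis.
5. Do not use a raw change score instead, and do not require a cue-colour factor.

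The cost is wording only. No new data or participants are needed. The common-slope covariate uses one degree of freedom of 96, and the interaction model uses three.
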